32.2.5 Handling and Disposal

The Investigator or designee will be responsible for dispensing and accounting for all investigational drug provided by Bristol-Myers Squibb (BMS), exercising accepted medical and pharmaceutical practices. Study drugs must be handled as cytotoxic agents and appropriate precautions taken per the institution's environmentally safe handling procedures. All investigational drugs will be dispensed in accordance with the Investigator's prescription or written order.

All products dispensed will be recorded on a product accountability record. Records of product lot numbers and dates received will be entered on a product accountability form. This record will be reviewed by the Supporter's staff or representative during periodic monitoring visits. It is the Investigator's responsibility to ensure that an accurate record of investigational drug issued and returned is maintained.

Used vials (excess drug) will be destroyed according to standard practices after properly accounting for the dispensing. Partially used vials of study drug will not be re-used for other participants.

Under no circumstances will the Investigator supply investigational drug to a third party or allow the investigational drug to be used in a manner other than as directed by this protocol.

32.3 Decitabine

Decitabine is commercially available and will be dispensed per standard of care. Decitabine will not be provided by this study and will be paid for by the patient's insurance carrier as part of the standard of care treatment.

PROTOCOL TITLE: I 49217 - Phase 1 CDX-1401/ Poly-ICLC +Decitabine +Nivolumab in Patients with MDS or Low Blast Count AML

34 APPENDICES/SUPPLEMENTS

PROTOCOL TITLE: I 49217 - Phase 1 CDX-1401/ Poly-ICLC +Decitabine +Nivolumab in Patients with MDS or Low Blast Count AML

**Appendix A ELIGIBILITY VERIFICATION FORM:
INCLUSION CRITERIA**

Participant Name: (Network sites use participant initials): _____

Medical Record No.: (Network sites use participant ID): _____

Title: A Phase 1 Study of DEC205mAb-NY ESO 1 Fusion Protein (CDX-1401) given with Adjuvant Poly-ICLC in Conjunction with 5-Aza-2'deoxyctidine (Decitabine) and Nivolumab in Patients with MDS or Low Blast Count AML

INCLUSION CRITERIA				
Yes	No	N/A	All answers must be "Yes" or "N/A" for participant enrollment.	Date
			1. Have a confirmed diagnosis of: a. IPSS intermediate-1, intermediate-2 or high-risk MDS including Chronic Myelomonocytic Leukemia (CMML) OR b. Low blast count AML with $\leq 30\%$ blasts previously classified as Refractory Anemia with excess blasts in transformation.	
			2. Age ≥ 18 years of age.	
			3. Have an ECOG Performance Status of ≤ 2 . Refer to Appendix "C".	
			4. Have adequate organ function defined by the following laboratory values: • Hepatic: o Total bilirubin ≤ 3 X upper limit of normal (ULN) (except subjects with Gilbert Syndrome, who can have total bilirubin up to 3.5 X ULN) o Aspartate Transaminase (AST/SGOT) and Alanine Transaminase (ALT/SGPD) ≤ 3 X ULN • Renal: o Serum creatinine ≤ 2.5 X ULN • Cardiac: o Troponin-I, CK-MB \leq ULN o LVEF \geq LLN (institutional limit)	
			5. Participants of child-bearing potential must agree to use adequate contraceptive methods (e.g., hormonal or barrier method of birth control; abstinence) prior to study entry, for the duration of study participation, and for 6 months after the last treatment. Should a woman become pregnant or suspect she is pregnant while she or her partner is participating in this study, she should inform her treating physician immediately.	
			6. Participant or legal representative must understand the investigational nature of this study and sign an Independent Ethics Committee/Institutional Review Board approved written informed consent form prior to receiving any study related procedure.	
			7. No prior exposure to nivolumab.	

PROTOCOL TITLE: I 49217 - Phase 1 CDX-1401/ Poly-ICLC +Decitabine +Nivolumab in
Patients with MDS or Low Blast Count AML

INCLUSION CRITERIA				
Yes	No	N/A	All answers must be "Yes" or "N/A" for participant enrollment.	Date
			8. No prior investigational therapy within 2 weeks prior to study enrollment	

Investigator Signature: _____ **Date:** _____

Printed Name of Investigator: _____

PROTOCOL TITLE: I 49217 - Phase 1 CDX-1401/ Poly-ICLC +Decitabine +Nivolumab in Patients with MDS or Low Blast Count AML

**Appendix B ELIGIBILITY VERIFICATION FORM:
EXCLUSION CRITERIA**

Participant Name: (Network sites use participant initials): _____

Medical Record No.: (Network sites use participant ID): _____

Title: A Phase 1 Study of DEC205mAb-NY ESO 1 Fusion Protein (CDX-1401) given with Adjuvant Poly-ICLC in Conjunction with 5-Aza-2'deoxyctidine (Decitabine) and Nivolumab in Patients with MDS or Low Blast Count AML

EXCLUSION CRITERIA				
Yes	No	N/A	All answers must be "No" or "N/A" for participant enrollment.	Date
			1. Subjects with life-threatening illnesses other than MDS, uncontrolled medical conditions or organ system dysfunction which, in the investigator's opinion, could compromise the subject's safety, or put the study outcomes at risk.	
			2. AML associated with inv(16); t(16;16); t(8;21) or t(15;17).	
			3. Previously untreated MDS with isolated del5q (for which lenalidomide is approved an approved therapy) and chronic myelomonocytic leukemia (CMML) with rearrangements of the PDGF receptor (for which imatinib is approved therapy), unless they have previously failed these approaches.	
			4. Subjects with symptomatic central nervous system (CNS) disease which is not adequately controlled	
			5. Subjects who have received prior radiation therapy for extramedullary disease within 2 weeks of first dose.	
			6. Has known immunosuppressive disease (e.g. HIV, AIDS or other immune depressing disease). Testing is not required, only to be done for a possible diagnosis which is not confirmed.	
			7. Uncontrolled intercurrent illness including, but not limited to, ongoing or active infection, symptomatic congestive heart failure, unstable angina pectoris, cardiac arrhythmia, or psychiatric illness/social situations that would limit compliance with study requirements. In addition, subjects will be excluded for any of the following: 
 • Myocardial infarction or arterial or venous thromboembolic events within 6 months prior to baseline or severe or unstable angina, New York Heart Association (NYHA) Class III or IV disease • Active congestive heart failure (New York Heart Association functional classification III or IV). • Documented history of cardiomyopathy with EF < 30%. • Uncontrolled hypertension (SBP > 160/DBP > 100 despite medical intervention). • History of myocarditis of any etiology 	
			8. Subjects who have hypersensitivity to decitabine, CDX-1401, poly-	

PROTOCOL TITLE: I 49217 - Phase 1 CDX-1401/ Poly-ICLC +Decitabine +Nivolumab in Patients with MDS or Low Blast Count AML

EXCLUSION CRITERIA				
Yes	No	N/A	All answers must be "No" or "N/A" for participant enrollment.	Date
			ICLC or nivolumab.	
			9. History of auto-immune disease (e.g., thyroiditis, lupus), except vitiligo.	
			10. Pregnant or nursing female subjects.	
			11. Unwilling or unable to follow protocol requirements.	
			12. Any condition which in the Investigator's opinion deems the participant an unsuitable candidate to receive study drug.	
			13. Regular use of immunosuppressant drugs such as steroids (>20mg prednisone equivalents), azathioprine, tacrolimus, cyclosporine, etc. Use is not permitted within 4 weeks before recruitment.	

Participant meets all entry criteria: Yes No

If "NO", do not enroll participant in study.

Investigator Signature: _____ **Date:** _____

Printed Name of Investigator: _____

PROTOCOL TITLE: I 49217 - Phase 1 CDX-1401/ Poly-ICLC +Decitabine +Nivolumab in
Patients with MDS or Low Blast Count AML

Appendix C ECOG Performance Status Scores

Description	Status
Fully active, able to carry on all pre-disease performance without restriction.	0
Restricted in physically strenuous activity but ambulatory and able to carry out work of a light or sedentary nature, e.g., light housework, office work.	1
Ambulatory and capable of all self-care but unable to carry out any work activities.	2
Capable of only limited self-care, confined to bed or chair more than 50% of waking hours.	3
Completely disabled. Cannot carry on any self-care. Totally confined to bed or chair.	4
Dead	5

PROTOCOL TITLE: I 49217 - Phase 1 CDX-1401/ Poly-ICLC +Decitabine +Nivolumab in Patients with MDS or Low Blast Count AML

Appendix D Response Criteria for MDS and AML According to Modified International Working Group Criteria

Response Criteria for MDS and AML patients according to modified IWG criteria	
Designation	Criteria for Response
Morphologic Leukemia Free state	<5% blasts in the marrow
Complete Response (CR)	Morphologic CR: BM blasts <5% with no dysplasia, in combination with CBC demonstrating: 1) platelets > 100K/mm ³ , 2) neutrophils > 1000/mm ³ Cytogenetic CR: As above + cytogenetics normal Molecular CR: As above + Molecular testing negative
Partial Remission (PR)	For MDS: BM blasts decreased by ≥50%, or less advanced MDS FAB classification than pretreatment. For AML: Blasts decreased by ≥50% or decrease to 5-25; Blasts ≤ 5% if Auer rod positive Platelets >100,000
Stable Disease (SD)	No PR, but no evidence of progression ≥ 2 months
Hematological Improvement (HI)	Erythroid Response (HI-E) 1) Major: Transfusion independence or 2g increase in Hg 2) Minor: 1 to 2g increase in Hg or 50% decrease in transfusion requirements Platelet Response (HI-P) 1) Major: absolute increase in platelets of 30K/mm ³ or development of transfusion independence 2) Minor 50% increase, net 10-30K/mm ³ Neutrophil Response (HI-N) 1) Major: 100% increase or absolute increase ≥500/mm ³ 2) Minor: 100% increase with value ≤500/mm ³

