Appendix E International Prognostic Scoring System for MDS

Variable					
Score	0	0.5	1.0	1.5	2.0
BM Blasts	<5	5-10		11-20	31-30
Karyotype	Good	Intermediate	Poor		
Cytopenias	0/1	2/3			

Risk Group	Score	Med Survival (y)	25% AML progression (y)
Low	0	5.7	9.4
Int-1	0.5-1.0	3.5	3.3
Int-2	1.5-2.0	1.1	1.1
High	>2.5	0.4	0.2

- Cytopenias are designated by the following: ANC<1800, platelets< 100K, Hg<10g
- Karyotype risk groups:
 - Good: Normal (46 XX or 46 XY), isolated -Y, isolated del(5q), or isolated del(20q)
 - Intermediate: All karyotypes not otherwise designated good or poor
 - Poor: complex karyotype (≥3 abnormalities) or any chromosome 7 abnormalities

PROTOCOL TITLE: I 49217 - Phase 1 CDX-1401/ Poly-ICLC +Decitabine +Nivolumab in Patients with MDS or Low Blast Count AML

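### Appendix D sets no red-cell condition for complete response, and several of its hematological improvement rules can be met in a lineage that was normal at entry

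*Combined protocol and SAP*

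**What the plan says.** Sections 1.3 and 8.3 record, as an exploratory and descriptive endpoint, a response rate made up of CR, PR and HI. Sections 8.3 and 11.4 read blood counts on day 1 of each cycle. Sections 11.7, 11.8, 16 and 19.3 all refer to Appendices D to F for the criteria, and no other section adds a condition.

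In Appendix D, morphologic CR is "BM blasts <5% with no dysplasia, in combination with CBC demonstrating: 1) platelets > 100K", followed by "2) neutrophils > 1000/mm" (per cubic millimetre). Nothing follows on haemoglobin or transfusion. Cytogenetic and molecular CR add to this definition and so inherit it. The PR row is split into MDS and AML; the CR row is not.

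The HI rows read:
- Erythroid, major: "Major: Transfusion independence or 2g increase in Hg". Erythroid, minor: "Minor: 1 to 2g increase in Hg or 50% decrease in transfusion requirements".
- Platelet, major: "1) Major: absolute increase in platelets of 30K", or transfusion independence that the text says must have developed. Platelet, minor: a 50% increase with a net gain of 10-30K.
- Neutrophil, major: a doubling, or an absolute rise of at least 500. Neutrophil, minor: a doubling with the value at or below 500.

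Appendix E, for prognostic scoring only, states: "Cytopenias are designated by the following: ANC<1800, platelets< 100K, Hg<10g".

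**The concern.** A response criterion in a cytopenic disease should show that something abnormal has got better. Two parts of Appendix D do not ensure this. CR checks two of the three blood lineages, although the protocol treats anaemia as part of the disease: Appendix E counts it as a cytopenia, Appendix D has an erythroid improvement row, and Section 10.1.3 expects red-cell transfusion dependence on study. Several HI rules credit a rise from any starting point, so ordinary variation in a normal count can be scored as a major response.

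At stake is what the one composite response rate means, and whether two assessors would score the same patient alike. The wording difference between the erythroid and platelet rows invites different scores for a patient who never needed red cells.

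**Working it through.** The plan states no power or precision figure for response, so there is nothing to reproduce. The check applies the printed rules to test patients.

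**1. CR.** Marrow blasts 3%, no dysplasia, platelets 120K, neutrophils 1200, haemoglobin 7 g, on red-cell transfusion. All printed conditions are met, so the patient is CR. This mainly changes the CR count. In MDS, any such patient who started at 6% blasts or more has also met the PR rule of a 50% fall (3 is at most half of 6), and would be in the combined rate anyway.

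**2. HI from normal baselines.**
- Haemoglobin 14 g to 14 g, never transfused: meets the major erythroid rule as worded.
- Platelets 250K to 280K: rise 30K, major.
- Neutrophils 4000 to 4500: rise 500, major.

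**3. Rules that are not affected.**
- Platelet minor: a 50% increase of at most 30K needs a baseline of at most 30/0.5 = 60K.
- Neutrophil minor: a doubling that ends at or below 500 needs a baseline of at most 500/2 = 250.
- A 50% fall in transfusion requirement presupposes transfusion at baseline.

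**4. Can such patients enrol?** Section 3.1 admits IPSS Int-1 or higher, which is a score of 0.5 or more. With 0 or 1 cytopenias (cytopenia score 0), the total is blast score (0, 0.5, 1.5 or 2.0) plus karyotype score (0, 0.5 or 1.0). Of the 4 x 3 = 12 combinations, only blasts <5% with good karyotype falls below 0.5, so 11 of 12 qualify. For example, 5-10% blasts with good karyotype scores 0.5. A patient with 0 or 1 cytopenias has at least two lineages that Appendix E does not call abnormal.

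**5. Weight of one patient.** 1/18 = 5.6 percentage points; two are 11.1 and three are 16.7.

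**6. Chance rises (illustration only).** Assume no true change, independent normal readings and within-person coefficient of variation CV. Then P(rise of at least t) = 1 - Φ(t / (baseline x CV x √2)). The last column, for any of four day 1 visits against one baseline, is by simulation.

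| Lineage, baseline | CV assumed | One visit | Any of 4 visits |
|---|---|---|---|
| Neutrophils 2500, t = 500 | 15% / 20% / 30% | 17% / 24% / 32% | 40% / 51% / 61% |
| Platelets 150K, t = 30K | 8% / 12% | 4% / 12% | 11% / 30% |
| Platelets 250K, t = 30K | 8% / 12% | 14% / 24% | 35% / 51% |

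Sensitivity for neutrophils at 2500, CV 15-30%:
- Requiring two consecutive qualifying visits out of four lowers 40-61% to 13-29%.
- If the true count at the visit is 20% lower (mean 2000), the single-visit chance is 1 - Φ(1000 / √((2500 CV)² + (2000 CV)²)), which is 2-15%.
- If it is 40% lower (mean 1500), the same formula with 1500 in the numerator and as the second mean gives less than 0.1% to 4%.

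**The case against.** The strongest reply is that nothing turns on this rate. Section 19.3 rules out comparison with historical controls, and Section 15 bases a larger study on immune responses without toxicity. That stands, and it limits the weight of the point. It does not make the definition right: a descriptive rate is only as informative as its rule.

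A reader might infer that response is the trial's only clinical-activity figure. It is not. Section 1.3 also records OS, PFS and time to AML transformation, and Section 8.3 adds molecular residual disease; none depends on these rules.

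A reader might also take the chance-rise percentages as the false responder rate to expect. The documents do not support that. Section 10.1.3 calls grade 4 neutropenia expected, and Table 2 shows grade 3 or higher neutropenia in 6 of 9 patients in the earlier vaccine and decitabine study, so falling counts would push the figures down. No section says that the best of several visits counts, and Section 16 grades objective responses every fourth cycle. Part of the figure comes from unconfirmed readings: at an abnormal baseline of 1700, the same model still gives 8-24% per visit, so a baseline condition alone would not remove chance responses.

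The literal erythroid reading can be called strained, since the row is headed as improvement. Fair, but the platelet row says what the erythroid row omits, so the ambiguity is in the text.

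Finally, Appendix E does not contradict Appendix D. Its limits serve prognostic scoring, and the CR neutrophil limit of 1000 already differs from its 1800. Using those limits for response is a choice, not a correction of an inconsistency. Appendix D is described as modified and cites publications that may carry further conditions; these cannot be consulted here, and Sections 16 and 19.3 make the appendix the operative detail.

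**Conclusion.** The point holds on the printed text, in limited form. CR has no haemoglobin or transfusion condition in either disease. The erythroid haemoglobin rises, platelet major rise and neutrophil major rule have no baseline condition, and the major erythroid rule read literally includes never-transfused patients. It would go too far to say that all HI rules lack a baseline condition: platelet minor, neutrophil minor and the transfusion-reduction rule already imply an abnormal or transfused start.

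The certain size is 5.6 percentage points of the response rate per misclassified patient, if 18 are evaluated. How many there will be cannot be derived from the documents, because it depends on baseline counts and transfusion history. The chance-rise figures show direction only. The effect is on one exploratory, descriptive rate; the primary DLT analysis, OS, PFS and time to AML transformation are untouched. An amendment is worthwhile because it is cheap.

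**What to change.** For response scoring only, in Appendix D:

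- **CR:** add a haemoglobin limit and a transfusion-free condition with a stated period, or report CR with and without them.
- **HI:** score it only in lineages abnormal at baseline. The Appendix E limits (haemoglobin <10 g, platelets <100K, neutrophils <1800) can serve unless the sponsor states others. Report HI by lineage, as responders over patients evaluable for that lineage.
- **Erythroid major rule:** require that transfusion independence be newly gained by a patient who was transfusion-dependent at baseline, and define transfusion dependence.

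Cost: the Appendix D wording; a baseline flag per lineage from counts already taken; and recording of transfusion status at baseline and on study, which Section 11.2 and Appendix J do not list. HI denominators will be smaller and the reported response rate may fall. Treatment, visits and sample size do not change.

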1.3 Exploratory Objectives

- To record the response rate (Complete Response, Partial Response and Hematological Improvement) in MDS or low blast count AML patients treated with the combination in order to provide descriptive characteristics.
- To record the Overall Survival (OS), Progression Free Survival (PFS) and time to AML transformation (TTT) (for patients with MDS at diagnosis) enrolled on the study.

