3 INCLUSION AND EXCLUSION CRITERIA

3.1 Inclusion Criteria

Subjects who present with a suspected or confirmed diagnosis of MDS/AML, and who are interested in potential participation on a clinical trial, will be screened for enrollment. Only patients who are willing to sign a written informed consent form will be screened. Patients must undergo bone marrow aspirate and biopsy with sample acquisition for protocol screening.

To be included in this study, participants must meet the following criteria:

1. Have a confirmed diagnosis of:

PROTOCOL TITLE: I 49217 - Phase 1 CDX-1401/ Poly-ICLC +Decitabine +Nivolumab in
Patients with MDS or Low Blast Count AML

- a. IPSS intermediate-1, intermediate-2 or high-risk MDS including Chronic Myelomonocytic Leukemia (CMML) **OR**
 - b. Low blast count AML with $\leq 30\%$ blasts previously classified as Refractory Anemia with excess blasts in transformation.
2. Age ≥ 18 years of age.
 3. Have an ECOG Performance Status of ≤ 2 . Refer to **Appendix C**.
 4. Have adequate organ function defined by the following laboratory values:
 - Hepatic:
 - Total bilirubin ≤ 3 X upper limit of normal (ULN) (except subjects with Gilbert Syndrome, who can have total bilirubin up to 3.5 X ULN)
 - Aspartate Transaminase (AST/SGOT) and Alanine Transaminase (ALT/SGPD) ≤ 3 X ULN
 - Renal:
 - Serum creatinine ≤ 2.5 X ULN
 - Cardiac:
 - Troponin-I, CK-MB \leq ULN
 - LVEF \geq LLN (institutional limit)
 5. Participants of child-bearing potential must agree to use adequate contraceptive methods (e.g., hormonal or barrier method of birth control; abstinence) prior to study entry. Should a woman become pregnant or suspect she is pregnant while she or her partner is participating in this study, she should inform her treating physician immediately.
 6. Participant or legal representative must understand the investigational nature of this study and sign an Independent Ethics Committee/Institutional Review Board approved written informed consent form prior to receiving any study related procedure.
 7. No prior exposure to nivolumab.
 8. No prior investigational therapy within 2 weeks prior to study enrollment.

Refer to **Appendix A** for the **ELIGIBILITY VERIFICATION FORM: INCLUSION CRITERIA** checklist.

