8.3 Exploratory Endpoints

- To record the response rate (Complete Response (CR), Partial Response (PR) and Hematological Improvement (HI)) in MDS or low blast count AML patients treated with the combination in order to provide descriptive characteristics.
 - This will be assessed using results of blood counts on day 1 of each cycle.
 - A formal assessment of response will be performed Day 1 of Cycle 5 and every 4th cycle thereafter as long as patients remain on decitabine and at end of study including results of blood counts and a bone marrow biopsy. After 2 years on study, bone marrow assessments may be done every 6 cycles rather than every 4 cycles. Retrospective response assessment will include measurement of molecular measurable residual disease at serial time points.

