19.3 Efficacy Analysis

All efficacy evaluations will be for correlative measures of immune response. Given the small sample size it will be impossible to compare responses with historical controls or speculate about the response over and above the historical response anticipated with single agent decitabine. Objective responses will be recorded and graded using the International Working Group Criteria for MDS and modified International Working Group Criteria for AML as detailed in Appendix D, Appendix E and, Appendix F.

PROTOCOL TITLE: I 49217 - Phase 1 CDX-1401/ Poly-ICLC +Decitabine +Nivolumab in Patients with MDS or Low Blast Count AML

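### Appendix D scores an MDS partial response on a 50% blast fall with no minimum starting level, so an unchanged patient entering with under 5% blasts can be recorded as a responder through counting error

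*Combined protocol and SAP*

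**What the plan says.** Appendix D gives the MDS rule for PR as: "For MDS: BM blasts decreased by ≥50%, or less advanced MDS FAB classification than pretreatment". It names no starting blast level, no absolute fall, no confirmation and no duration. The AML lines follow in the same cell, which ends with "Platelets >100,000". The same table puts the leukemia-free state, and the blast part of complete response (CR), at marrow blasts below 5%.

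Section 3.1 admits MDS at IPSS Int-1, Int-2 or high risk and sets no minimum blast percentage. In Appendix E, blasts below 5% score 0, so a patient can qualify on karyotype and cytopenias alone.

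PR is one part of an exploratory endpoint in section 8.3: "To record the response rate (Complete Response (CR), Partial Response (PR) and Hematological Improvement (HI)) in MDS or low blast count AML patients". On timing, the same section says: "A formal assessment of response will be performed Day 1 of Cycle 5 and every 4th cycle thereafter". Sections 11.7, 16 and 19.3 refer response grading to the appendices and add no floor or confirmation rule. Section 19.3 limits what response can be used for: "Given the small sample size it will be impossible to compare responses with historical controls".

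**The concern.** A relative fall is a stable measure only when the starting value is large compared with its counting error. At 2% blasts, a 200-cell differential rests on about four blasts, and a repeat count of two or fewer meets the 50% rule. A patient whose disease has not moved can then be called a partial responder.

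The category also fits these patients poorly. They are below the 5% blast level that Appendix D uses for its better response categories before any treatment is given, so a further halving says little. Stable disease is defined as the absence of PR, so a PR produced by noise also displaces the correct label.

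What is at stake is the accuracy of the reported rate of CR, PR and hematological improvement (HI). With at most 18 evaluable patients and no control arm, nothing in the data would reveal such an error.

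**Working it through.** The plan states no error rate for PR, so there is no figure of its own to reproduce.

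**Step 1: can patients with under 5% blasts enter?** Appendix E points with blasts at 0:

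| Karyotype | 0/1 cytopenias | 2/3 cytopenias |
|---|---|---|
| Good (0) | 0, Low | 0.5, Int-1 |
| Intermediate (0.5) | 0.5, Int-1 | 1.0, Int-1 |
| Poor (1.0) | 1.0, Int-1 | 1.5, Int-2 |

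Five of the six combinations are eligible under section 3.1.

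**Step 2: chance of a false PR.** Inputs: true blast fraction p, the same at both times; n cells counted (not in the documents; 200 and 500 assumed). The baseline count X and each follow-up count Y are independent Binomial(n, p). The rule is met when X ≥ 1 and Y ≤ X/2, so for k assessments against one baseline, with any PR counted:

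P = Σ (x ≥ 1) P(X = x) × [1 − (1 − P(Y ≤ ⌊x/2⌋))^k]

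Main terms for n = 200, p = 2%, k = 1:

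| x | P(X = x) | P(Y ≤ ⌊x/2⌋) | product |
|---|---|---|---|
| 2 | 0.1458 | 0.0894 | 0.0130 |
| 3 | 0.1963 | 0.0894 | 0.0175 |
| 4 | 0.1973 | 0.2351 | 0.0464 |
| 5 | 0.1579 | 0.2351 | 0.0371 |
| 6 | 0.1047 | 0.4315 | 0.0452 |
| 7 | 0.0592 | 0.4315 | 0.0256 |
| 8 | 0.0292 | 0.6288 | 0.0183 |

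These give 0.203. The remaining terms bring the total to 0.218.

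All results, with cycles 5 and 9 as the two assessments:

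| True blasts | 200 cells, one | 200 cells, two | 500 cells, one | 500 cells, two |
|---|---|---|---|---|
| 1% | 31.9% | 48.9% | 18.3% | 31.1% |
| 2% | 21.8% | 36.3% | 8.2% | 14.9% |
| 3% | 15.2% | 26.3% | 4.0% | 7.5% |
| 4% | 10.9% | 19.4% | 2.0% | 3.8% |
| 8% | 3.1% | 5.9% | 0.1% | 0.2% |

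**Step 3: effect on the reported rate.** One false PR in 18 patients adds 1/18 = 5.6 percentage points if that patient has no CR or HI, and nothing otherwise. The number entering below 5% is not given. As an illustration only, suppose 6 of 18 enter at a true 2%. One assessment then gives 6 × 0.082 = 0.5 expected false PRs with 500 cells, or 6 × 0.218 = 1.3 with 200. The chance of at least one is 1 − (1 − 0.082)^6 = 40% or 1 − (1 − 0.218)^6 = 77%.

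**Step 4: with a floor.** Restricting the sum to a recorded baseline of at least 5% (x ≥ 0.05n), one assessment:

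| True blasts | 200 cells | 500 cells |
|---|---|---|
| 1% | 0.0% | 0.0% |
| 2% | 0.6% | 0.0% |
| 3% | 3.9% | 0.3% |
| 4% | 7.1% | 1.2% |

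What remains comes from baselines that read high by chance. At 4% and 200 cells over two assessments, the fall is from 19.4% to 12.1%.

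**The case against.** The strongest reply is that nothing depends on this endpoint. Response is exploratory and descriptive, section 19.3 rules out comparison with historical controls, and section 15 bases the case for a larger study on immune responses without toxicity. That is correct, and it limits the weight of the point. It does not make the definition sound, because a descriptive rate should still describe response.

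The platelet line may apply to the whole PR cell. It is printed after the AML text, so AML only is the natural reading, but the layout is uncertain after conversion from PDF. If it covers MDS, fewer unchanged patients would qualify, since platelets below 100K are one of the qualifying cytopenias. It would still set no blast floor, and an unchanged patient already above 100K could score PR.

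The cell count is assumed, and at 4% blasts with 500 cells the chance is only 2% per assessment. The two-assessment figures also require that any single PR counts, and the documents do not define best response. Both limits stand.

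Appendix D is headed as modified International Working Group criteria, and the cited sources may contain further conditions. They cannot be checked here, but sections 16 and 19.3 send the assessor to the detail in the appendices.

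A reader might also infer that the FAB limb is faulty because a small move across a class boundary would suffice. The documents give no FAB boundaries and so no way to compute such a probability. Requiring a 50% blast fall alongside it would only repeat the other limb. No change to that limb is asked for.

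**Conclusion.** The gap is real and its consequence is limited. As written, Appendix D lets an eligible MDS patient with under 5% blasts and no true change be scored PR. The one-assessment chance runs from 2% (true 4%, 500 cells) to 32% (true 1%, 200 cells). Over two assessments, if any PR counts, it runs from 4% to 49%. These figures rest on binomial counting error, independent counts and an assumed number of cells. Marrow sampling and reader differences are not modelled.

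It would be tempting to conclude that the trial's clinical signal is inflated. The documents do not support that. They do not say how many patients will enter below 5%; that 7 of 9 patients in the predecessor study had MDS says nothing about their blast levels. A false PR also raises the combined rate only in a patient without CR or HI. The DLT endpoint, the decision rules, the sample size and the marker tests are untouched.

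**What to change.** In the PR row of Appendix D, apply the MDS blast-fall limb only when recorded baseline marrow blasts are at least 5%, the level the table already uses for CR. Score MDS patients recorded below 5% by CR and HI only. State whether the platelet condition applies to MDS as well as AML. Leave the FAB limb as it is.

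The floor works well at true blasts of 1–2% and only partly at 4%, because some baselines will read high.

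The cost is a few words in one appendix, with no new visit, sample or patient. The downside is fewer PRs and a departure from the current Appendix D wording, which should be stated when results are reported.
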